5.2. Adverse Events of Special

Adverse events of special interest to be summarized include the following:

Major Hemorrhage

Hemorrhage SMQ without labs will be used to identify bleeding events. Any grade ≥ 3 hemorrhage events, any SAE or all grades of CNS hemorrhage (preferred terms are listed in Appendix A). Events will be summarized by preferred terms.

5.3. Adverse Events of Clinical Interest

Other Malignancies

New malignant tumors including solid tumors, skin malignancies and hematologic malignancies that occur after study treatment initiated will be identified and summarized by preferred terms and toxicity grade. Terms to be extracted are determined through cumulative AE term reviews.

Atrial Fibrillation

Cardiac events – Atrial fibrillation will be extracted by preferred terms. The number and percentage of subjects who had events will be summarized by preferred terms.

Ocular Events

Ocular events will be extracted and summarized separately by preferred terms.

Immune-related AEs (irAEs): Endocrine, Gastrointestinal, Hepatic, Hypersensitivity/Infusion Reaction, Pulmonary, Renal, Skin, and Visual Events

Immune-related events will be extracted (as below) and summarized separately by preferred terms.

CATEGORY	SUBCATEGORY	PREFERRED TERMS
ENDOCRINE ADVERSE EVENT	ADRENAL DISORDER	ADRENAL UNSUFFICIENCY
		ADRENAL SUPPRESSION
		BLOOD CORTICOTROPHIN DECREASED
		BLOOD CORTICOTROPHIN INCREASED
		HYPOTHALAMIC PITUITARY ADRENAL AXIS SUPPRESSION
		SECONDARY ADRENOCORTICAL INSUFFICIENCY
	DIABETES	DIABETES MELLITUS
		DIABETIC KETOACIDOSIS
		FULMINANT TYPE 1 DIABETES MELLITUS
		LATENT AUTOIMMUNE DIABETES IN ADULTS
		TYPE 1 DIABETES MELLITUS
	PITUITARY DISORDER	HYPOPHYSITIS
	THYROID DISORDER	AUTOIMMUNE THYROIDITIS
		BLOOD THYROID STIMULATING HORMONE DECREASED
		BLOOD THYROID STIMULATING HORMONE INCREASED
		HYPERTHYROIDISM
		HYPOTHYROIDISM
		PRIMARY HYPERTHYROIDISM
		PRIMARY HYPOTHYROIDISM
		THYROID FUNCTION TEST ABNORMAL
		THYROID HORMONES DECREASED
		THYROID HORMONES INCREASED
		THYROIDITIS
		THYROIDITIS ACUTE
		THYROXINE DECREASED
		THYROXINE FREE DECREASED
		THYROXINE FREE INCREASED
		THYROXINE INCREASED
		TRI-iodothyronine UPTAKE INCREASED

GASTROINTESTINAL ADVERSE EVENT	AUTOIMMUNE COLITIS COLITIS COLITIS ULCERATIVE DIARRHOEA ENTERITIS ENTEROCOLITIS FREQUENT BOWEL MOVEMENTS GASTROINTESTINAL PERFORATION
HEPATIC ADVERSE EVENT	ACUTE HEPATIC FAILURE ALANINE AMINOTRANSFERASE INCREASED ASPARTATE AMINOTRANSFERASE INCREASED AUTOIMMUNE HEPATITIS BILIRUBIN CONJUGATED INCREASED BLOOD ALKALINE PHOPHATASE INCREASED BLOOD BILIRUBIN INCREASED DRUG-INDUCED LIVER INJURY GAMMA-GLUTAMYLTRANSFERASE INCREASED HEPATIC ENZYME INCREASED HEPATIC FAILURE HEPATITIS HEPATITIS ACUTE HEPATOTOXICITY HYPERBILIRUBINAEMIA LIVER DISORDER LIVER FUNCTION TEST ABNORMAL LIVER INJURY TRANSAMINASES INCREASED
HYPERSENSITIVITY/INFUSION REACTION	ANAPHYLACTIC REACTION ANAPHYLACTIC SHOCK BRONCHOSPASM HYPERSENSITIVITY INFUSION RELATED REACTION
PULMONARY ADVERSER EVENT	ACUTE RESPIRATORY DISTRESS SYNDROME ACUTE RESPIRATORY FAILURE INTERSTITIAL LUNG DISEASE LUNG INFILTRATION PNEUMONITIS
RENAL ADVERSER EVENT	ACUTE KIDNEY INJURY BLOOD CREATININE INCREASED BLOOD UREA INCREASED CREATININE RENAL CLEARANCE DECREASED HYPERCREATININAEMIA NEPHRITIS NEPHRITIS ALLERGIC

SKIN ADVERSE EVENT

NEPHRITIS AUTOIMMUNE
 RENAL FAILURE
 RENAL TUBULAR NECROSIS
 TUBULOINTERSTITIAL NEPHRITIS
 URINE OUTPUT DECREASED
 AUTOIMMUNE DERMATITIS
 BLISTER
 DERMATITIS
 DERMATITIS EXFOLIATIVE
 DRUG ERUPTION
 ECZEMA
 ERYTHEMA
 ERYTHEMA MULTIFORME
 EXFOLIATIVE RASH
 PALMAR-PLANTAR ERYTHRODYSAESTHESIA SYNDROME
 PHOTSENSITIVITY REACTION
 PRURITUS
 PRURITUS ALLERGIC
 PRURITUS GENERALISED
 PSORIASIS
 RASH
 RASH ERYTHEMATOUS
 RASH GENERALISED
 RASH MACULAR
 RASH MACULO-PAPULAR
 RASH PAPULAR
 RASH PRURITIC
 SKIN EXFOLIATION
 SKIN HYPOPIGMENTATION
 SKIN IRRITATION
 STEVENS-JOHNSON SYNDROME
 TOXIC EPIDERMAL NECROLYSIS
 URTICARIA
 VITILIGO
 UVEITIS
 VISION BLURRED
 ENDOPHTHALMITIS
 PHOTSENSITIVITY REACTION
 VISUAL IMPAIRMENT
 PHOTOPSIA
 VISUAL FLOATERS
 PHOTOPHOBIA
 DIPLOPIA

VISUAL AE

Adverse events of interest and other safety observations will be summarized by disease type and study cohorts.

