Cardiac events: Atrial fibrillation and atrial flutter have been reported in patients treated with ibrutinib, particularly in patients with cardiac risk factors, acute infections, and a previous history of atrial fibrillation. There is no evidence of QT prolongation with increasing doses of ibrutinib.

Other malignancies: Other malignancies, most frequently skin cancers (18/357 subjects or 5%), have occurred in patients treated with ibrutinib.

Rash: Rash has been commonly reported in subjects treated with either single agent ibrutinib or in combination with chemotherapy. Most rashes were mild to moderate in severity. Rash has been commonly reported in subjects treated with either single agent ibrutinib or in combination with chemotherapy. Rash occurred at a higher rate in the ibrutinib arm than in the ofatumumab arm in a randomized, comparator-controlled study, Study 1112. Most rashes were mild to moderate in severity. One case of Stevens-Johnson Syndrome (SJS), with a fatal outcome, was reported in a subject with CLL. The subject received ibrutinib (420 mg/day) and was also receiving various antibiotics and antigout medication (allopurinol) known to be associated with SJS.

Tumor lysis syndrome: TLS has been reported with ibrutinib therapy.

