- subject refuses further therapy
- investigator's decision to withdraw the subject
- pregnancy of the subject
- noncompliance with study treatment or procedure requirements

The average duration of study therapy is expected to be approximately 6 months.

In Part A of the study, a SET, consisting of the principal investigators, sponsor medical monitors, and the sponsor's clinical pharmacologist, or their designees, and the sponsor statistician will review all available data upon completion of the first 2 treatment cycles (ie, 4 weeks of study therapy) for all subjects at each dose cohort to determine DLTs, if dose escalation is acceptable, and ultimately to determine the recommended Phase 2 dose.

In Part B of the study, all subjects in each cohort may be evaluated for response by the SET and additional functional representatives from Janssen, as applicable. The SET along with optional other internal members may review safety on an ad hoc basis, and efficacy endpoints (including but not limited to ORR).

The End-of-Treatment Visit will occur within 30 days after the last dose of ibrutinib or nivolumab, whichever treatment occurred last.

During the Follow-up Period, long-term safety, survival status, disease progression, subsequent anticancer therapy, and occurrence of other primary malignancy data will be collected as well as anti-drug antibody (ADA) sampling if applicable. During the Follow-up Period, subjects should be followed for safety up to 30 days after the last dose of ibrutinib or 100 days after the last nivolumab infusion, whichever is later. The safety follow-up includes adverse event reporting and laboratory assessments (at the first follow-up). Thereafter, follow-up visits will be completed approximately every 3 months until death or the end of study. Subjects who have developed treatment-related Grade 3 or higher toxicity at the end of treatment will be assessed until recovery to Grade ≤ 1 or baseline, deemed irreversible, or until end of study. Adverse events leading to

discontinuation will be followed up until resolution or return to baseline, or end of study, whichever occur first.

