13.1. Definitions

13.1.1. Adverse Event Definitions and Classifications

Adverse Event

An adverse event is any untoward medical occurrence in a clinical study subject administered a medicinal (investigational or non-investigational) product. An adverse event does not necessarily have a causal relationship with the treatment. An adverse event can therefore be any unfavorable and unintended sign (including an abnormal finding), symptom, or disease temporally associated with the use of a medicinal (investigational or non-investigational) product, whether or not related to that medicinal (investigational or non-investigational) product. (Definition per International Conference on Harmonisation [ICH])

This includes any occurrence that is new in onset or aggravated in severity or frequency from the baseline condition, or abnormal results of diagnostic procedures, including laboratory test abnormalities.

Note: The sponsor collects adverse events starting with the signing of the ICF (refer to Section 13.3.1, All Adverse Events, for time of last adverse event recording).

Serious Adverse Event

A serious adverse event based on ICH and EU Guidelines on Pharmacovigilance for Medicinal Products for Human Use is any untoward medical occurrence that at any dose:

- Results in death
- Is life-threatening
(The subject was at risk of death at the time of the event. It does not refer to an event that hypothetically might have caused death if it were more severe.)
- Requires inpatient hospitalization or prolongation of existing hospitalization
- Results in persistent or significant disability/incapacity
- Is a congenital anomaly/birth defect
- Development of a new malignancy that is not associated with the disease under study
- Is a suspected transmission of any infectious agent via a medicinal product
- Is Medically Important*

*Medical and scientific judgment should be exercised in deciding whether expedited reporting is also appropriate in other situations, such as important medical events that may not be immediately life threatening or result in death or hospitalization but may jeopardize the subject or may require intervention to prevent one of the other outcomes listed in the definition above. These should usually be considered serious.

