13.3. Procedures

13.3.1. All Adverse Events

All adverse events and special reporting situations, whether serious or non-serious, will be reported from the time a signed and dated ICF is obtained until 30 days after the last dose of ibrutinib or 100 days after the last nivolumab infusion, whichever is later. Afterwards, report only SAEs that are at least possibly related to study treatment. After the clinical cutoff, only SAEs and Grade ≥ 3 AEs will be collected. Serious adverse events, including those spontaneously reported to the investigator within 30 days after the last dose of study therapy, must be reported using the Serious Adverse Event Form. The sponsor will evaluate any safety information that is spontaneously reported by an investigator beyond the time frame specified in the protocol.

Disease progression should not be recorded as an adverse event or serious adverse event term; instead, signs and symptoms of clinical sequelae resulting from disease progression/lack of efficacy will be reported if they fulfill the serious adverse event definition (refer to Section 13.1.1). Death should not be recorded as an adverse event or serious adverse event, but as the outcome of an adverse event. The event that resulted in the death should be reported as a serious adverse event.

All events that meet the definition of a serious adverse event will be reported as serious adverse events, regardless of whether they are protocol-specific assessments.

All adverse events, regardless of seriousness, severity, or presumed relationship to study drug, must be recorded using medical terminology in the source document and eCRF; reporting on eCRF after CCO (per amendment #6 and 7 further revisions apply per [Table 1](#)[collection of SAEs and Grade ≥ 3 AEs, AEs leading to discontinuation or modification, laboratory assessments {Grade ≥ 3 or clinically significant}]). Whenever possible, diagnoses should be given when signs and symptoms are due to a common etiology (eg, cough, runny nose, sneezing, sore throat, and head congestion should be reported as "upper respiratory infection"). Investigators must record in the eCRF their opinion concerning the relationship of the adverse event to study therapy. All measures required for adverse event management must be recorded in the source document and reported according to sponsor instructions.

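### SAP 5.3 finds other malignancies through AE terms only, while the protocol contradicts itself on whether late malignancies judged unrelated are reported

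*SAP*

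**What the plan says.** SAP 5.3 lists other malignancies as an adverse event of clinical interest. It covers solid, skin and hematologic tumors "that occur after study treatment initiated will be identified and summarized by preferred terms and toxicity grade". No closing date or relatedness condition is attached. The one step it gives for finding cases is "Terms to be extracted are determined through cumulative AE term reviews".

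The AE data behind that step are governed by Protocol 13.3.1. All AEs are reported "until 30 days after the last dose of ibrutinib or 100 days after the last nivolumab infusion, whichever is later". The next rule is "Afterwards, report only SAEs that are at least possibly related to study treatment". A further sentence covers the later phase: "After the clinical cutoff, only SAEs and Grade ≥ 3 AEs will be collected".

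Three other places bear on the same cases:

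- Protocol 13.1.1 includes among its criteria for a serious event: "Development of a new malignancy that is not associated with the disease under study".
- Protocol 13.3.2 asks sites to report every serious event during the study within 24 hours, with no causality condition.
- Protocol 3.1 says that in the Follow-up Period "subsequent anticancer therapy, and occurrence of other primary malignancy data will be collected". SAP 1.2 repeats this. Neither attaches a causality condition.

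Protocol 1.2.2 gives the reason for interest: "Other malignancies, most frequently skin cancers (18/357 subjects or 5%), have occurred in patients treated with ibrutinib".

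**The concern.** The summary described in SAP 5.3 and the data feeding it do not have the same scope. The summary is open-ended and blind to causality. Under 13.3.1 the data are blind to causality only until the safety window closes. After that, the investigator's causality judgment decides whether a new malignancy becomes an AE record. The protocol promises a second source, the follow-up malignancy data, that would not depend on that judgment, but no SAP section says it will be analyzed.

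At stake is the interpretability of one named safety summary. A single count would mix two kinds of ascertainment, and the share of follow-up under the stricter rule would differ between cohorts, because SAP 1.2 expects median treatment to run from about 2 months in DLBCL to 15 months in CLL. Cohorts with short treatment would have the least complete capture. The study has no control arm, so a reader comparing the rate with ibrutinib experience elsewhere would not know what window it refers to. The primary endpoint is not affected.

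**Working it through.** The plan gives no figure to reproduce. The check is a comparison of texts plus one illustrative calculation.

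**Is a malignancy that arises after the window and is judged unrelated captured?**

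| Place | Answer |
|---|---|
| Protocol 13.3.1, rule after the window | No: serious events only if at least possibly related |
| Protocol 13.3.1, sentence on the period after clinical cutoff | Unclear: serious and Grade 3 or higher events, relatedness not mentioned |
| Protocol 13.3.2 with 13.1.1 | Yes: a new malignancy is serious, and all serious events are reported |
| Protocol 3.1 and SAP 1.2 | Yes: collected in follow-up, by a route not described |
| Protocol Table 1 | AE row stops at the End-of-Treatment visit; no row for other malignancies |
| Protocol 3.1, minimum eCRF list after cutoff | Other malignancies not named |
| SAP 5.1, treatment-emergent definition | Events outside the window kept only if related; window also closes when subsequent systemic therapy starts |
| SAP 5.3 | In scope by its wording, but only AE term review is named |

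SAP 5.3 does not say whether its tables are limited to treatment-emergent events. If they are, SAP 5.1 applies the same causality filter a second time.

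**Direction.** If 13.3.1 governs, the AE data contain all malignancies inside the window plus the at-least-possibly-related ones outside it. That is a subset of what 5.3 describes, so the count equals the intended count or falls below it.

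**Illustration of the exposed time.** Inputs: expected median treatment of 2 months in DLBCL and 15 months in CLL (SAP 1.2); 1 month = 30.4375 days (SAP 2.7); 100 days after nivolumab (Protocol 13.3.1). Assumption: both drugs stop together, so the 100-day limit is the later one.

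- Extension: 100 / 30.4375 = 3.29 months.
- DLBCL: full capture ends at 2 + 3.29 = 5.29 months after first dose.
- CLL: full capture ends at 15 + 3.29 = 18.29 months.

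For a DLBCL subject at the median, time outside full capture is:

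- with 6 months of follow-up (the interval to the primary analysis for the last subject): 6 − 5.29 = 0.71 months, and 0.71 / 6 = 12%;
- with 12 months of follow-up (the 1-year time point for PFS and OS): 12 − 5.29 = 6.71 months, and 6.71 / 12 = 56%.

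For a CLL subject at the median, neither follow-up length reaches the end of full capture.

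**The case against.** The strongest reply is that the protocol, read as a whole, already requires these cases. Section 13.3.2 asks for all serious events during the study, 13.1.1 makes a new malignancy serious, and 3.1 says the data are collected. The SAP sentence on term review can also be read as describing how the list of terms is built, not as limiting the data source or the time span. The case report form is not among the documents, so follow-up malignancies may be entered as AE records, in which case 5.3 would already include them, or on a separate form.

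Much of this stands. A reader might infer that late unrelated malignancies are certain to be lost. The documents do not support that: they give conflicting instructions, and a case missing from the AE data could still be in the database. What remains is that 13.3.1 is the rule written specifically for the period after the window, it says only related serious events are reported, and SAP 5.3 names no source that would compensate.

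A reader might also want a number missed. Applying the 5% from Protocol 1.2.2 to all subjects gives 0.05 × 158 = 7.9, but that is an expected total borrowed from another population, not the number falling outside the window and judged unrelated. Similarly, 56% holds only under an assumed 12 months of follow-up; at 6 months the same calculation gives 12%. The documents say nothing about how long second malignancies take to appear or how often investigators judge them unrelated, so no argument here rests on either.

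Finally, this is a descriptive summary. Protocol 13.3.3 names only major hemorrhage as an event of special interest, and no decision rule depends on the malignancy count. That limits the consequence but does not remove the inconsistency.

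**Conclusion.** The point holds as a conflict between sections and an unstated data source in SAP 5.3, not as demonstrated loss of data. If 13.3.1 is followed and 5.3 is programmed from AE terms alone, the malignancy table omits cases after the window that are judged unrelated, and any error is downward. The number omitted cannot be derived from the documents. The exposed follow-up can be illustrated only under assumptions: for a DLBCL subject stopping both drugs at the expected 2-month median, about 0.7 of 6 months or 6.7 of 12 months. The conclusion does not depend on those figures; it follows from the texts.

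**What to change.** In SAP 5.3, state that other malignancies are identified from both the AE data and the other-primary-malignancy data collected in follow-up, regardless of relationship to study drug and of time since last dose. Report the number of subjects with a new malignancy inside and outside the 30/100-day window, each with its person-time. Say explicitly that this summary is not restricted to treatment-emergent events as defined in SAP 5.1.

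In the protocol, reconcile 3.1, 13.3.1, 13.3.2 and Table 1 on whether malignancies after the window that are judged unrelated are reported, and where they are recorded.

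The SAP change costs a few sentences and minor extra programming, and draws on data the protocol already says are collected. Changing 13.3.1 or Table 1 is more costly: it needs a formal amendment with ethics committee approval under Protocol 18.1, and Amendments 6 and 7 deliberately reduced data collection. If the protocol is left as it is, the SAP should at least state the source and window used and note that capture after the window may depend on causality.

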- Drug-related sepsis
- Drug-related respiratory failure secondary to pneumonitis and progressive disease

After database lock for the final CSR, 2 subjects were reported to have died; both were subjects with NSCLC treated with 3-mg/kg nivolumab. The reported causes of death for these 2 subjects were:

- Drug-related pneumonitis
- Non-drug-related infection after experiencing drug-related Grade 3 pneumonitis

Although not considered to be the primary cause of death in all 5 subjects described above, pneumonitis was considered a contributory factor in each case.

Preliminary new non-clinical safety findings of adverse pregnancy outcomes and infant losses in the absence of overt maternal toxicity have been reported. The findings of increased late stage pregnancy loss and early infant deaths/euthanasia in nivolumab exposed pregnant monkeys suggest a potential risk to human pregnancy if there is continued treatment with nivolumab during pregnancy.

Additional details on the safety profile of nivolumab, including results from other clinical studies, are also available in the BMS-936558 (nivolumab) Investigator Brochure (IB).

Adverse Event Management Algorithms

Because of the potential for clinically meaningful nivolumab-related AEs requiring early recognition and prompt intervention, management algorithms have been developed for suspected pulmonary toxicity, gastrointestinal, hepatotoxicity, endocrinopathy, skin toxicity, neurological toxicity, and nephrotoxicity.

The algorithms recommended for utilization are contained in Section 8 of the protocol.

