| Adverse Event | CTCAE Grade | Ibrutinib and Nivolumab |
| Endocrinopathy | Section 8.3. (Table 12): Management of Endocrinopathies | |
| | Asymptomatic | Continue study therapy. |
| | Symptomatic | Abnormal lab values and pituitary MRI scan: Hold study therapy until improvement to Grade ≤ 1 ; resume at same dose and schedule. |

Table 8: Dose Adjustments for Related Non-hematologic and Related Hematologic Toxicities

| | | |
|-------------------------------------|---|---|
| | Suspicion of adrenal crisis | Hold study therapy; discontinue study therapy if no improvement after adrenal hormone replacement. |
| Rash | Section 8.4. (Table 13): Management of Rash | |
| | Grade 1 | Continue study therapy. |
| | Grade 2 | Persistent ^a ≤12 weeks: Continue therapy at same dose and schedule. Persistent ^a >12 weeks: Discontinue study therapy |
| | Grade 3 | Hold study therapy until resolution to ≤ Grade 1 Persistent >2 weeks or inability to reduce steroid ≤10 mg/day >12 weeks: Discontinue study therapy. Discontinue if Grade 3 rash recurs. |
| | Grade 4 | Discontinue study therapy |
| Neurological | Section 8.6. (Table 15): Management of Neurological Adverse Events | |
| | Grade 1 | Continue study therapy. |
| | Grade 2 | Hold study therapy until improvement to Grade ≤1; then resume study therapy. |
| | Grade 3 and 4 | Discontinue study therapy. |
| Uveitis or visual complaints | Section 8.8. (Table 17): Management of Uveitis and Visual Complaints | |
| | Grade 1 | Consider hold study therapy. |
| | Grade 2 | Hold study therapy until improvement to Grade ≤1; then resume study therapy. Persistence for >2 weeks from day of onset despite symptomatic treatment: Discontinue study therapy. |
| | Grade 3 and 4 | Discontinue study therapy. |

- a. Persistent treatment-related adverse event that do not recover to Grade ≤1 within 12 weeks after last dose of nivolumab.

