8.6. Neurological Adverse Events

Neurological AEs have been uncommonly observed following treatment with nivolumab. Neurological AEs can manifest as central abnormalities (eg, aseptic meningitis or encephalitis) or peripheral sensory/motor neuropathies (eg, Guillain-Barre Syndrome). The onset has been observed as early as after a single treatment. Early recognition and treatment of neurologic AEs is critical to their management. Subjects should be advised to seek medical evaluation if they notice impairment in motor function (eg, weakness), changes in sensation (eg, numbness), or symptoms suggestive of possible central nervous system abnormalities such as new headache or mental status changes.

Table 15: Management of Neurological Adverse Events

| Management and Follow-up of Neurological Adverse Events. For dose modification guidelines, refer to Table 8 and Table 9. | |
|---|--|
| Grade 1 | Monitor per protocol Worsening: treat as \geq Grade 2 |
| Grade 2 | Immediately: treat symptoms according to institutional standards; consider 0.5-1.0 mg/kg/d methylprednisolone IV or oral equivalent Worsening: treat as Grade 3-4 |
| Grade 3-4 | Immediately: consult neurologist; treat symptoms according to institutional standards; start 1.0-2.0 mg/kg/d methylprednisolone IV or IV equivalent; prophylactic antibiotics Worsening or atypical presentation: consider immunoglobulins IV (IVIG) or other immunosuppressive therapies according to institutional standards Improvement to \leq Grade 2: taper steroids over at least 1 month |
| General | Patients on IV steroids may be switched to an equivalent dose of oral corticosteroids (eg, prednisone) at start of tapering or earlier, once sustained clinical improvement is observed. The lower bioavailability of oral corticosteroids need to be considered |

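### The SAP's immune-related AE list has no neurological category, so neurological irAEs that the protocol manages would not be counted in that summary if they occur

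*SAP*

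**What the plan says.** SAP 5.3 covers immune-related AEs under the heading "Immune-related AEs (irAEs): Endocrine, Gastrointestinal, Hepatic, Hypersensitivity/Infusion Reaction, Pulmonary, Renal, Skin, and Visual Events". The rule is that "Immune-related events will be extracted (as below) and summarized separately by preferred terms", followed by a table of preferred terms in those eight categories. For other malignancies the same section uses an open rule: "Terms to be extracted are determined through cumulative AE term reviews". No such provision is made for irAEs, and no rule uses the investigator's view that an event is immune-related.

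SAP 5.1 also lists immune-related events among the groups that receive the standard AE summary, but it neither defines them nor refers to 5.3.

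On the protocol side:

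- Section 1.3.2 says management algorithms exist for a list of nivolumab toxicities that ends "endocrinopathy, skin toxicity, neurological toxicity, and nephrotoxicity".
- Section 8.6, in the chapter on managing immune-related AEs and AEs of clinical interest, says: "Neurological AEs can manifest as central abnormalities (eg, aseptic meningitis or encephalitis) or peripheral sensory/motor neuropathies (eg, Guillain-Barre Syndrome".
- Table 9 in Section 6.4.3, the dose-adjustment table for immune-related AEs, has a neurological row that points to "Section 8.6. (Table 15): Management of Neurological Adverse Events" and calls for discontinuation at Grades 3 and 4.

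**The concern.** The safety profile of the combination is a secondary objective, and the irAE summary is where a reader would look for added immune toxicity. A summary built only from the listed terms has no place for neurological events, so its silence could be read as showing that none occurred.

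These events can be serious for the subject and for the trial. Under Table 9 a Grade 3 or 4 neurological event ends study therapy. Under protocol Section 3.3.1 a related event that requires discontinuation in the DLT window of Part A qualifies as a DLT once the Study Evaluation Team confirms it. An event of that weight could be absent from the one table meant to collect immune toxicity.

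**Working it through.** The point rests on no sample size, power or alpha figure, so there is no stated number to reproduce. The check compares lists.

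**Step 1: contents of the SAP list.** Entries in the 5.3 table by category:

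| Category | Entries |
|---|---|
| Endocrine | 29 |
| Gastrointestinal | 8 |
| Hepatic | 19 |
| Hypersensitivity/infusion reaction | 5 |
| Pulmonary | 5 |
| Renal | 12 |
| Skin | 29 |
| Visual | 9 |

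The total is 29 + 8 + 19 + 5 + 5 + 12 + 29 + 9 = 116. One term, photosensitivity reaction, stands under both skin and visual, which leaves 115 distinct terms. Searching the entries for the stems ENCEPHAL, MENING, GUILLAIN, NEURO, MYASTHEN and DEMYELIN returns nothing. The heading sentence itself names the eight categories without a neurological one, so the gap is not caused by a table being misread from PDF.

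**Step 2: Table 9 against the SAP categories.**

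| Protocol Table 9 row | SAP 5.3 category |
|---|---|
| Infusion reaction | Hypersensitivity/infusion reaction |
| Enterocolitis or diarrhea | Gastrointestinal |
| Renal/creatinine | Renal |
| Pneumonitis | Pulmonary |
| Hepatic alteration; AST/ALT and bilirubin | Hepatic |
| Endocrinopathy | Endocrine |
| Rash | Skin |
| Uveitis or visual complaints | Visual |
| Neurological | none |

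Apart from the general irAE row at the top, neurological is the only row without a SAP category.

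**Step 3: could another SAP rule pick these events up as immune-related?** SAP 5.1 promises an immune-related summary but gives no definition, so 5.3 is the only operational one. SAP Appendix A contains two encephalitis-type terms (haemorrhagic encephalitis and acute haemorrhagic leukoencephalitis), but only to identify CNS bleeding for the major-hemorrhage analysis.

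**Step 4: where would such an event be seen?** SAP 5.1 tabulates all treatment-emergent AEs by system organ class and preferred term, and by severity, relationship and action taken. It repeats the summary for drug-related AEs, serious AEs, drug-related serious AEs, AEs leading to discontinuation, and death. A neurological event would be in the first of these and in each of the others for which it qualifies.

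**Step 5: is the omission explained by a wish for specificity?** The SAP gives no rationale, and the list already accepts non-specific terms such as diarrhoea, rash, blood creatinine increased and vision blurred.

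**The case against.** The best counter-argument has three parts.

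First, the protocol is not uniform. Section 13.2.1 lists nivolumab events of clinical interest by name (colitis, endocrine, uveitis, hepatic, pneumonitis, renal, skin) and does not name neurological events. That list resembles the SAP's categories, and SAP 5.3 carries the clinical-interest title. Nor does placement in Section 8 prove that an event is immune-related, since that chapter also covers infection and lipase or amylase elevations. This stands as far as it goes. But the 13.2.1 list ends with immune-related AEs as a catch-all, so it does not exclude neurological events, and Table 9 is explicitly an immune-related table with a neurological row.

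Second, SAP 5.1 does not say that its immune-related summary is limited to the 5.3 list. That is correct. A reader might infer that such events are certain to be missing from all irAE results; the documents support this only for 5.3, and for 5.1 only if the same list is used.

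Third, the events remain visible elsewhere. This also stands. A reader might infer that they vanish from the report, or survive only as scattered terms in the general tables, and Step 4 shows otherwise. Still, the same could be said of the eight categories that are listed; the purpose of the irAE summary is to bring such events into one count.

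Two further inferences should be resisted. Nothing in the documents shows that a neurological irAE has occurred. And the list entry spelled ADRENAL UNSUFFICIENCY is a matter for proofreading; that it would defeat extraction is a guess about programming.

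**Conclusion.** The point holds in limited form. Followed as written, SAP 5.3 would not count a neurological irAE, and 5.1 would not either if it shares that definition. The irAE count would then be understated by however many subjects had such an event and no other listed term. No data are lost, and the primary endpoint is untouched.

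The size in subjects cannot be stated. Section 8.6 describes these events only as uncommon. Section 1.3.2 names the drug-related Grade 3-4 terms seen in more than 2 of 306 subjects on nivolumab alone, and none is neurological. That implies at most 2/306 = 0.65% for any single such term. It limits neither the neurological category as a whole, nor lower grades, nor the combination, so it should not be turned into an expected count for the planned 158 subjects.

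The conclusion assumes that the printed list is applied as the SAP states. It is a worthwhile alignment of the SAP with the protocol, affecting a descriptive safety summary.

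**What to change.** In SAP 5.3, add a neurological category to the heading and the table, with pre-specified preferred terms for the events in Section 8.6: aseptic meningitis, encephalitis, Guillain-Barre syndrome, and peripheral sensory or motor neuropathies. Show non-specific neuropathy terms on a separate line. Protocol Section 1.2.2 lists peripheral sensory neuropathy among the frequent events with ibrutinib plus chemo/immunotherapy, and such terms could otherwise dominate the category.

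In SAP 5.1, state that the immune-related summary uses the 5.3 definition.

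Correct the spelling of the adrenal insufficiency term in the same pass.

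The cost is a short wording change and one more category in an existing table, using AE data already collected. The reported irAE rate may rise slightly.
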